5.4.3 Early Termination

An enrolled/vaccinated subject may be terminated from the study for any of these reasons:

- a) Subject withdraws consent.
- b) PI or a medical monitor involved in the study decides that termination is in the best interest of the subject.
- c) PI or a medical monitor involved in the study decides that termination is necessary to protect the integrity of the study or achieve the objectives of the study.
- d) Interruption of study schedule makes the subject's data unusable according to protocol requirements.
- e) Sponsor terminates the study.
- f) Governing IRBs recommends to terminate the study

If a subject withdraws from the study for any reason prior to the planned study duration, every attempt is made to complete the following:

- a) Report of local and systemic reactogenicity and AEs are reviewed by PI (or designee).
- b) Obtain specimens for immunogenicity analysis if withdrawal occurs prior to scheduled laboratory testing.
- c) Diary Card information is reviewed with the subject in detail by site staff, if in use since the last visit.
- d) Injection site(s) examination and a targeted physical examination are performed (if indicated).

IVAC must be informed within 48 hours of all instances of the premature termination of a subject's participation in the trial.

If the subject develops a reaction to study vaccine which the investigator believes threatens the subject's well-being, the withdrawn subject must be treated or transferred to a treatment facility.

Study Termination: IVAC retains the right to temporarily suspend or prematurely discontinue this study at any time related to safety. If the study is stopped or suspended prematurely, IVAC will inform the local Principal Investigator as well as regulatory authorities about the decision and the reasons for termination or suspension. If such action is taken, all efforts must be made to ensure the safety of the subjects enrolled in the study. The Principal Investigator will assist IVAC in informing the responsible IEC and provide the reason for the suspension or termination. In case of premature study or study site closure, the monitor will conduct all activities for final monitoring visits.

6 Study Products

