3.2.2 Safety Endpoints

The safety profile of IVACFLU-A/H5N1 will be evaluated by the proportion of subjects experiencing AEs, related or not related, of the following five categories for all subjects and by age group (18-40 years of age and 41-60 years age):

- Number and percentage of subjects with solicited local and systemic adverse events within 30 minutes after each vaccination.
- Number and percentages of subjects with solicited local adverse events (redness, swelling, pain, induration, and tenderness) over a 7-day period (Days 1-7; Days 22-28) post each vaccination.
- Number and percentages of subjects with solicited systemic/general adverse events (fever, fatigue/malaise, muscle aches (generalized), joint aches, chills, nausea, vomiting, and headache) over a 7-day period (Days 1-7; Days 22-28) post each vaccination.
- Number and percentages of subjects with unsolicited adverse events for 21 days post each vaccination.
- All serious adverse events (SAEs) occurring over the entire study period. (Days 1-91).

4 Study Design

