14. On Day 91 (+/- 10 days) subjects will be contacted by phone for (a) closure of any ongoing AEs and concomitant medications; and (b) collection of any SAEs and new concomitant medications, if associated with the SAE reported. This will complete subject participation in the study and subjects will be exited from the study, however, if the subject reports any health problems, the PI may use his or her medical judgment and ask the participant to come to the clinic for an examination or any necessary testing.

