9.2.8 Serious Adverse Events

An SAE is defined as an AE that meets one of the following conditions:

- Death.
- Life-threatening (subject at immediate risk of death). (*This means that the subject was at risk of death at the time of the event; it does not refer to an event that hypothetically might have caused death if it were more severe.*)
- Requires inpatient hospitalization or prolongation of existing hospitalization.
- Results in congenital anomaly/birth defect. (*Only in the case of a woman becoming pregnant during the study period after administration of at least one injection of study product. All pregnancies must be followed to term and outcome reported to IVAC and regulatory agencies.*)
- Results in a persistent or significant disability or incapacity.
- Important medical events that might not result in death, be life-threatening, or require hospitalization might be considered SAEs when, based upon appropriate medical judgment, the event might jeopardize the well-being of the subject and require medical or surgical intervention to prevent one of the outcomes listed above. (*Medical and scientific judgment should be exercised in deciding whether reporting these events is appropriate.*)

All SAEs must be reviewed and evaluated by a study clinician (SAE relationship to study vaccine must be evaluated as outlined in Section 9.2.3) and recorded on an SAE form and reported, as specified in Section 9.3. All such SAEs should also be followed until satisfactory resolution or until the investigator deems the event to be chronic or the patient to be stable.

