9.4 Duration of Follow Up for AE Resolution

All reported AEs should be followed until resolution or stabilization, or until the subject's participation in the study ends. Subjects who have an ongoing study product-related SAE at study completion or at discontinuation from the study will be followed by the PI, or his/her designee, until the event is resolved or determined to be irreversible, chronic, or stable by the PI.

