All screened subjects who provide informed consent, regardless of the subject's randomization and treatment status in the trial.

B. Full Analysis (FA) Population

All subjects in the enrolled population who were randomized, received a study vaccination. This population will serve as the primary analysis population for all safety objectives. The immunogenicity analysis based on this population will serve as the supportive results for all immunogenicity objectives. Subjects who withdraw or are terminated from the study will be included in the FA data set until the time of withdrawal or termination. Subjects will be analyzed as received; that is, allocation errors, if any, are taken into account.

C. Per Protocol (PP) Population

All subjects in the Full Analysis population who have valid baseline (Day 1)¹ and a post-vaccination immunogenicity measure with no major protocol violations that are determined to potentially interfere

¹ The protocol does not state this requirement.

with the immunogenicity assessment of the study vaccine (e.g., missed the 2nd vaccination). This population will serve as the primary analysis population for all immunogenicity objectives.²

The criteria for exclusion of subjects from the Full Analysis Population and Per Protocol Population will be established by the study statistician and the study medical officer before breaking the blind and will be based on the blinded review of protocol violations.

III. MISSING DATA

In the event that missing visit dates or study contact dates are needed to be imputed for couples of study forms, the following rules will be applied:

- The month and year are known, but the date was missing, the 15th was used for any calculations of relative time (e.g., UNMAY2016 will become 15MAY2016).

For missing safety related data, the following rules will be applied:

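### Termination under 5.4.3 ends scheduled SAE ascertainment, and both SAPs cut the safety data at that point, although the SAE endpoint runs to Day 91

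*Protocol*

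**What the plan says.** - **Who can be terminated.** Protocol 5.4.3: "An enrolled/vaccinated subject may be terminated from the study for any of these reasons". The list includes consent withdrawal (a), the subject's best interest (b), study integrity or aims (c), an interrupted schedule (d: "Interruption of study schedule makes the subject's data unusable according to protocol requirements"), and study-wide stops (e, f). Grounds (b) to (d) need no withdrawal of consent.
- **What happens at exit.** Protocol 5.4.3: "If a subject withdraws from the study for any reason prior to the planned study duration, every attempt is made to complete the following". The items are an AE and reactogenicity review, an immunogenicity specimen, a diary review and an examination if indicated. No later contact is listed.
- **How late SAEs are found.** Protocol 4.6.3: "On Day 91 (+/- 10 days) subjects will be contacted by phone". Sections 4.6.3 and 7.3.10 make no provision for terminated subjects.
- **Follow-up of known events.** Protocol 9.4 stops AE follow-up when participation ends, with one exception: "Subjects who have an ongoing study product-related SAE at study completion or at discontinuation from the study will be followed by the PI". Protocol 9.2.8 is wider: it asks for follow-up of every SAE, related or not, to resolution or until the event is judged chronic or the subject's condition stable.
- **Analysis.** Section II.B of both the interim and the final Phase 3 SAP: "Subjects who withdraw or are terminated from the study will be included in the FA data set until the time of withdrawal or termination". This is the primary safety population.
- **Endpoint.** Protocol 3.2.2 and section VIII of both SAPs define SAEs over Days 1 to 91. They are summarised as simple percentages of subjects, with no adjustment for time observed.

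**The concern.** An interrupted schedule can spoil a Day 43 titre. It does not spoil the safety record of someone who has already been injected. The plan nevertheless uses one exit, termination from the study, for both purposes, and the SAPs then close the safety data at that exit.

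Safety is a primary objective, and the safety sample size in Protocol 12.2 rests on seeing at least one rare event. For such an endpoint, a subject observed for three weeks should not be counted in the same way as one observed for thirteen. Under grounds (b) to (d) the reason for leaving may itself be health-related. If it is, the unobserved time belongs disproportionately to people at higher risk, and the reported SAE proportion is too low.

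**Working it through.** **Inputs.** From Protocol 12.2: N = 1100 on the selected dose, true rate of related SAEs p = 0.21%, stated detection above 90%, stated zero-event 95% upper limit 0.33%. From the final SAP preface: 500 Phase 3 vaccinees on 15 mcg plus 100 from Phase 2, so 600. Endpoint window: 91 days. The documents give no termination rate, so 1% to 10% is assumed, at Day 22 (the Injection 2 visit), with SAE risk even over the window.

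**1. Reproduce the plan's figures.** Detection = 1 − (1 − p)^N = 1 − 0.9979^1100 = 90.1%. Zero-event upper limit = 1 − 0.025^(1/1100) = 0.335%. Both agree with the protocol.

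**2. Window lost per terminated subject.** L = (91 − 22)/91 = 69/91 = 75.8%. At Day 8 it would be 91%, and at Day 43 it would be 53%.

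**3. Loss unrelated to health.** With a fraction d terminated:
- share of SAEs unseen = d × L
- expected related SAEs unseen = 1100 × 0.0021 × d × L = 2.31 × d × L
- detection = 1 − (1 − p)^(N(1−d)) × (1 − p(1 − L))^(Nd)
- upper limit counting only fully followed subjects = 1 − 0.025^(1/(N(1−d)))

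| Terminated (assumed) | SAEs unseen | Expected related SAEs unseen | Detection, N=1100 | Zero-event upper limit, fully followed only |
|---|---|---|---|---|
| 0% | 0% | 0 | 90.1% | 0.335% |
| 1% | 0.8% | 0.02 | 89.9% | 0.338% |
| 2% | 1.5% | 0.04 | 89.7% | 0.342% |
| 5% | 3.8% | 0.09 | 89.2% | 0.352% |
| 10% | 7.6% | 0.18 | 88.2% | 0.372% |

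At 600 vaccinees, detection is 71.7% with no loss and 70.3% with 5% terminated. The zero-event upper limit is 0.61% with no loss and 0.65% on the 570 fully followed. The drop from 1100 to 600 is a separate matter: the final SAP cites protocol version 3.0, so it may be a version difference.

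**4. Loss linked to health (illustration only).** If terminated subjects carry k times the SAE risk of the others, the unseen share is d·k·L / (1 − d + d·k). With d = 5%:
- k = 1: 3.8%
- k = 2: 0.10 × 0.758 / 1.05 = 7.2%
- k = 5: 0.25 × 0.758 / 1.20 = 15.8%

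The documents give no value for k.

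**The case against.** The other side has several good points.

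- **Late SAEs are not barred from being reported.** Section 9.3.1 requires every SAE the site learns of to go to the sponsor, related or not. Subjects are told at the Day 1, 8, 22 and 29 visits to report later events needing care. Section 9.3.4 follows pregnancies to term. Section VIII of both SAPs says all SAEs will be listed. A reader might infer that SAEs after termination are never counted, but the documents do not support that. What stands is that nobody is assigned to ask, and that the Full Analysis wording excludes even a spontaneous report from the summaries.
- **A missed or delayed Injection 2 does not by itself end follow-up.** The final SAP treats a missed second dose as a Per Protocol exclusion. Section 7.3.5 withholds the injection after a positive pregnancy test without terminating the subject. Section 9.5.2 treats stopping product as its own decision. Termination under 5.4.3 is discretionary. This limits how many subjects are affected; it does not close the gap for those who are terminated.
- **Bias is not demonstrated.** A reader might infer that early leavers are sicker, or that the loss is greater in the vaccine arm. No data here show either. Phase 1 (75 subjects) had no SAEs and no discontinuation for an AE.
- **One missed event is not a measure of this problem.** The upper limits of 0.33% for 0/1100 and 0.51% for 1/1100 differ visibly, but any missed SAE from any cause would do the same. The expected number missed here is well below one.
- **Some exits legitimately end collection.** Consent withdrawal and study-wide termination do, and the SAP cut suits those cases. The avoidable loss lies under grounds (b) to (d).
- **Part of the reporting exists.** Both SAPs tabulate withdrawals with reasons, and the DSMB reviews completeness. Neither SAP reports the number with incomplete safety follow-up by arm.

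**Conclusion.** The point holds in a limited form. For a vaccinated subject terminated under grounds (b) to (d), the plan schedules no further search for new SAEs, and both SAPs, as worded, drop anything that starts later. The subject still counts as event-free over Days 1 to 91. This is a stated rule, not a missing detail.

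If termination is rare and unrelated to health, the cost is small: about 0.9 percentage points of detection at N=1100 with 5% terminated at Day 22, and under 2 points at 10%. Those rates, the Day 22 timing and even risk over the window are assumptions. If termination is linked to illness, the SAE proportion is biased low by an amount the documents cannot fix. Neither that link nor any difference between arms is shown. The change is still worth making, because the loss is avoidable and rare-event conclusions have little slack.

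The conflict between 9.4 and 9.2.8 is a related but separate wording problem. It concerns how long an SAE already known at discontinuation and judged unrelated is followed, not whether new ones are found.

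**What to change.** 1. **Protocol 5.4.3.** State that stopping injections, or exclusion from the Per Protocol set (including for the reasons in (c) and (d)), does not end safety data collection. Vaccinated subjects who have not refused contact keep the existing Day 43 AE/SAE review and Day 91 SAE call. Ask subjects who withdraw whether the Day 91 call is still acceptable.
2. **Both SAPs, II.B.** Replace the clause that ends inclusion at withdrawal or termination with all safety data collected through Day 91 (through Day 43 for the interim analysis). Report, by arm, how many subjects have incomplete safety follow-up.
3. **Protocol 9.4 and 9.2.8.** Reconcile the two statements on following ongoing SAEs after discontinuation, so that an SAE judged unrelated is handled in one way.

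The cost is wording in the protocol and both SAPs, plus one disposition line by arm. The visit and the call already exist, and few subjects should be affected.

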6.1 Study Product Descriptions

6.1.1 Study Vaccine

IVACFLU-A/H5N1 is an influenza A/H5N1 vaccine produced by IVAC using embryonated chicken eggs. IVACFLU-A/H5N1 is a whole virus vaccine, collected in a linear sucrose density gradient solution using a continuous flow centrifuge (Alfa Wassermann, West Caldwell, NJ) and inactivated with formaldehyde. Vaccine strain NIBRG-14 derived from original influenza A/ Vietnam/1194/2004 was provided to IVAC by the National Institute for Biological Standards and Control of the Health Protection Agency of the United Kingdom.

6.1.2 Formulation, Packaging and Labeling (Product Name and Trademark)

IVACFLU-A/H5N1 is formulated to contain either 15 mcg hemagglutinin (HA) and 0.6 mg of aluminum hydroxide adjuvant per 0.5 mL dose, or 30 mcg hemagglutinin (HA) and 0.6 mg of aluminum hydroxide adjuvant per 0.5 mL dose. It is filled in single dose vials. Each 0.5 mL dose may contain residual amounts of formaldehyde (not more than 0.02%) and sucrose (not more than 0.2%).

IVACFLU-H5N1 has a sterile, slightly opalescent suspension after shaking well. Antibiotics are not used in the manufacture of IVACFLU-A/H5N1. IVACFLU-A/H5N1 does not contain latex. The future package insert will describe the vaccine as follows:

Product name:	A/H5N1 Influenza vaccine
Trademark:	IVACFLU-A/H5N1
Active substance:	Virus particles containing hemagglutinin (HA)
Formulation:	15 mcg HA in 0.5 mL PBS pH 7.2 or 30 mcg HA in 0.5 ml PBS pH 7.2 Aluminum hydroxide 0.6 mg in 0.5 mL
Product form:	Purified whole virus, inactivated, with adjuvant (Aluminum Hydroxide).
Pharmaceutical form:	Injectable biologic
Administration route:	Intramuscular (IM)
Dosage:	0.5 mL, 2 injections, 21 days apart
Packaging:	10 single-dose vials per box*
Storage:	From + 2°C to + 8°C, avoid freezing

*Because of the need for blinding of vaccine and placebo, packaging in this trial may be different.

6.1.3 Placebo

[figure not shown]
Placebo (PBS) will be manufactured by IVAC. PBS, pH 7.2, will also be in 0.5 mL single-dose vials.

NaCl	4.500 mg
Na₂HPO₄.2H₂O	0.685 mg
NaH₂PO₄.2H₂O	0.186 mg
Water For Injection (qs)	0.5 mL

[figure not shown]
6.1.4 Packaging

IVACFLU-A/H5N1 vaccine and placebo will be filled in glass vials at a dose volume of 0.5 ml, and covered with a pharmaceutically acceptable rubber stopper, an aluminum cap seal, and single-use flip-off plastic lid. Packaging will be done to assure that the vials are intact and vaccine of high quality. A continuous temperature data logger will be placed inside each carton box to monitor product temperature during the process of transportation, storage, and delivery of the product. The carton boxes will also have “product to be used for clinical trial purposes only” label and information on the product storage temperature (from +2°C to +8°C). The sample label is below:

- Label of IVACFLU-A/H5N1 vaccine containing the 30 µg HA/dose (0.5 ml)

[figure not shown]
- Label of IVACFLU-A/H5N1 vaccine containing the 15 µg HA/dose (0.5 ml)

- Label of the Placebo

The study product must not be used if the package or labeling appears to be tampered with, the label is illegible, or the physical properties (color and transparency) are altered. These labels will be overlabeled with a blinded randomization code, similar to what is shown below.

6.1.5 Stability and Storage

Study product must be stored at a temperature between +2 degrees Celsius (°C) to +8°C. The shelf-life is 24 months in that condition. Storage temperature must be monitored daily and documented on an appropriate form. Back-up power or storage must be available in case of primary power failure. Study

vaccine and placebo must never be frozen. Their temperature will be monitored at the manufacturer, during transport, and at the clinical trial site.

In case of accidental disruption of the cold chain, the products may not be administered and the investigator or the responsible person should contact IVAC to receive further instructions. In such cases, the investigator must receive written consent (through facsimile or emailed, scanned copy) of IVAC before any study product may be used.

6.1.6 Lot Number, Expiry Date, and Quality Control Results of Study Vaccine Lots

The vaccine study lots and placebo study lots have passed quality control testing performed by the National Institute of Control Vaccine and Medical Biologicals, Vietnam. See Appendix C for the results.

6.2 Dosage, Preparation, and Administration of Study Products

6.2.1 Dosage and Schedule

Each dose will total 0.5 mL containing either 15 mcg or 30 mcg of HA, and delivered intramuscularly into the deltoid of the non-dominant arm. In this study, in order to monitor local reactions, each dose will be injected into the deltoid of the non-dominant arm, unless the deltoid of the non-dominant arm area is not ideal for injection/reactogenicity or the subject prefers the injection in the other arm.

Each dose will be administered 21 days apart in this study.

6.2.2 Precautions and Warnings

1. IVACFLU-A/H5N1 is only to be used for healthy adults 18 to 60 years of age participating in this study. It is forbidden to use the vaccine for any other purpose.
2. Strict compliance with the regulations of the MOH on the use of vaccines and biologicals is required (Decision No.12/2014/TT-BYT, dated 20/03/2014).
3. Vaccination of each 0.5 mL dose must be intramuscularly into the deltoid of the non-dominant arm, not intravenously or subcutaneously.
4. Study product vials that have been frozen may not be used.
5. IVACFLU-A/H5N1 or placebo solution is a homogenous preparation, transparent or clear white in appearance. Do not inject if the study product vial appears to have unusual content or if the liquid in the vials has changed color.
6. Only health workers who have been trained in the framework of this research may administer study product to subjects participating in the research, assuring proper intramuscular injection technique and sterile injection.
7. Only one person may be injected with one needle and syringe.

8. During vaccination, researchers must supervise vaccination activities and record observations of post-vaccination monitoring of subjects.
9. Study subjects must be monitored during vaccination and 30 minutes afterwards.
10. During study vaccinations, there must be adequate facilities for monitoring and treating any reactions. Drugs to treat anaphylaxis must be available, as must specialist doctors for such an emergency.

6.2.3 Preparation and Administration

To prepare and administer study product, vaccination facilities and investigators must comply with Ministry of Health regulations (No.12/2014/TT-BYT, dated 20/03/2014). The step-by-step instructions for the investigator are as follows:

1. Wash hands. Prepare the study vaccine/placebo, needles, syringes, and sharps safety box ahead of time.
2. In order to preserve the study blind, a qualified, specially trained staff member (nurse or physician) will prepare the study product for administration immediately before administration. This will be a different person than the one who evaluates reactogenicity of the subject. Specific study procedures will be developed, including selecting the appropriate vial for each subject, gently shaking the vaccine vial, withdrawing the 0.5-mL dose of study vaccine/placebo from the vial using a sterile needle and syringe, labeling the syringe with subject identification number, and occluding the contents of the syringe. Careful records must be maintained to ensure and document that each subject receives the correct dose. Once the dose vial has been penetrated, the withdrawn study vaccine/placebo should be used promptly.
3. Make sure you have sufficient equipment to provide every subject with a safe injection and to dispose of injection materials safely.
4. Make sure you have emergency drug and equipment kits in both the vaccination area and the observation area.
5. Greet the subject in a friendly manner. Ask whether he/she has any questions or concerns about immunization and respond to his/her questions or concerns in a truthful, pleasant manner.
6. Confirm the subject identity.
7. Ensure the subject is seated.
8. Ask the subject about his/her handedness and record this information on the CRF.
9. Inform the subject that for consistency in the study, all subjects will be vaccinated in the deltoid of the non-dominant arm.
10. Instruct the subject to put the non-dominant arm on the hip and show the deltoid of the non-dominant arm.
11. Disinfect the skin at the injection site.

12. Inject intramuscularly the entire contents of the syringe into the deltoid region of the upper non-dominant arm.
13. While the plunger is still depressed, remove the needle from the subject's arm.
14. Apply cotton swab with pressure to the injection site. Do not put sticking plaster onto the injection site.
15. Do not recap the needle. Dispose of the needle and syringe in a sharps container. Store the empty vial in a safe place (not the refrigerator) until the end of the study. The vial must not be disposed of until monitors have verified that it is allowed.
16. Record the date of vaccination and vaccine vial number on the subject's vaccination card.
17. Ask the subject to rest for 30 minutes.
18. While the subject is resting, explain how to use the Diary Card for recording any symptoms.
19. After 30 minutes, observe the subject and ask about the subject's well-being.

